## **10.4 Sensitivity analyses**

- **Outcomes measured by referred peers (actual):** Measure effect estimate for peer client PrEP outcomes (e.g., initiation, recent HIV testing, continuation) as reported by referred peers, among those we were able to reach for follow-up.
- **Outcomes among all potential referred peers (n=320):** Measure effect estimates for referred peer PrEP outcomes (e.g., initiation, recent HIV testing, continuation) as reported by index peers, but among all potential referred peers index peers were recommended to recruit (n=320 clients, 4 per index peer)
- **Continuation among referred peers that initiated PrEP:** Measure effect estimates for peer client PrEP continuation as reported by index peers, among referred peers that initiated PrEP.
- **Treat “don’t know” responses as successes.** Measure effect estimates for referred peer PrEP outcomes (e.g., initiation, recent HIV testing, continuation) reported by index peers, but assume all “don’t know” responses are successes versus failures.
- **Multiple imputation of “don’t know” responses** via Markov Chain Monte Carlo under the assumption of missingness at random.
- **GEE approach:** Measure effect size estimates for referred peer PrEP outcomes (e.g., initiation, recent HIV testing, continuation) as reported by peer provider using the generalized estimating equations.

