 904 predictor: study arm; standard errors adjusted for clustering by peer provider). All analyses comparing
 905 randomization arms will be intention-to-treat, complete case analyses conducted at the unit of the
 906 individual (either peer provider or peer client). The primary comparison will be formalized peer PrEP
 907 referral + HIVST delivery versus informal peer PrEP referral (the standard of care). For analyses
 908 conducted at the level of the peer client, we will adjust standard errors for clustering at the peer provider
 909 level. We will use mixed-effect logistic regression models to measure risk ratios. All statistical test with 2-
 910 sided p-values <0.05 will be considered statistically significant. We will complete all analyses in R and
 911 STATA.

912 *Sample size*

913 If we assume that peer providers refer 75% of the targeted peer clients, this leaves us with three clients
 914 per peer provider, or 240 peer clients in total. We performed power calculations for our primary outcome,
 915 the proportion of referred peer clients who initiated PrEP at three months, in Stata 16.1 using methods
 916 for cluster-randomized trials, where each cluster is a peer group of one peer provider and three peer
 917 clients (**Figure 10**). **Table 10** shows the power we have to attain to detect various increases in the
 918 proportion of peer clients who initiated PrEP in the formal peer PrEP referral arm + HIVST (intervention
 919 group) vs. the informal peer PrEP referral arm (standard of care group). For our power calculations, we
 920 assumed 40 clusters (peer providers) per arm, 3 sampling units (peer clients) per cluster, and an intra-
 921 cluster correlation coefficient (ICC) of 0.05, which is standard for cluster-randomized controlled trials.
 922

925

Fig. 10. Power calculation to detect increase in the percentage (%) of referred peer clients initiating PrEP in the intervention group.

926

927

Table 10. Increase in the % of referred peer clients initiating PrEP in the intervention group. ICC: 0.05; clusters (providers) per arm: 40; units (clients) per cluster: 3 (75% of suggested clients referred)

Power (%)	Standard of care (%), p1	Intervention (%), p2	Increase (%), p2-p1
70	30	46.3	16.3
	40	56.8	16.8
	50	66.5	16.5
	60	75.7	15.7
	70	84.1	14.1
	80	91.7	11.7
80	30	48.4	18.4
	40	58.9	18.9
	50	68.5	18.5
	60	77.5	17.5
	70	85.7	15.7
	80	92.9	12.9
90	30	51.4	21.4
	40	61.7	21.7
	50	71.2	21.2
	60	79.9	19.9
	70	87.8	17.8
	80	94.5	14.5

928

929

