## 3. Study overview and objectives

### 3.1. Study overview

**Table 1. Overview of the Peer PrEP cRCT components**

[figure not shown]
Protocol title:	Peer PrEP referral + HIV self-test delivery for PrEP initiation among young Kenyan women: randomized implementation trial
Short title:	Peer PrEP Study
Design:	This study is a hybrid effectiveness-implementation randomized trial
Population:	We will enroll two different population types in this study: 1. Index peers : (Also called PrEP users or peer providers in our formative research and pilot study). Adolescent girls and young women ≥16-24 years  old using PrEP for at least one month in the past 12 months.

	
2. Referred peers: (Also called peers or PrEP clients in our formative research and pilot study). Female peers <math>\geq 16</math>-24 years old of the index peer whom the index peer thinks has behaviors associated with HIV risk and may be interested in and benefit from daily oral PrEP.
 
16- and 17-year-olds must be emancipated minors; all participants must be able and willing to provide informed consent.

Randomization:	1:1 enhanced group: standard group

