**Table 3. Detailed description of Peer PrEP cRCT primary and secondary outcomes**

Outcome	Definition	Reported by	Timing
PrEP initiation*	% of referred peers that went to a clinic and were dispensed PrEP pills , among those referred	Index peers*	Month 3
Recent HIV testing	% of referred peers who tested for HIV (any form of testing, including HIVST) since peer PrEP referral, among those referred.	Index peers	Month 3
PrEP continuation	% of referred peers that returned to a clinic to refill PrEP , among those referred. 	Index peers	Month 3
	% of index peers that returned to a clinic to refill PrEP , in the past 3 months (i.e., since peer referral)	Index peers	Month 3
PrEP adherence	Median of Wilson et al's 0-100 point adherence score,  with higher scores indicating higher adherence 	Referred peers	Month 3

\* Primary outcome

In prior versions of the SAP (v1.5), this was conditional among clients who initiated PrEP, but we changed to make it unconditional to align with the intent-to-treat analysis plan (described below) and best RCT practices on 07/11/2024—prior to study unblinding—per the recommendation of our DSMB.

Wilson, I. B., et al. (2009). "Improving the self-report of HIV antiretroviral medication adherence: is the glass half full or half empty?" *Curr HIV/AIDS Rep* 6(4): 177-186.

In prior versions of this SAP (v1.4), we had suggested an adherence threshold based on the Wilson et al score, but on 3/22/2024—prior to study unblinding—we decided to turn this into a continuous outcome after observing low continuation and thus low adherence in the past month among referred peers in review of the aggregate data across study arms in our DSMB.

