#### **5. Sample size justification**

##### **5.1. Sample size calculation**

If we assume that index peers refer 75% of suggested referred peers, this leaves us with three clients per peer provider, or 240 referred peers in total. We performed power calculations for our primary outcome, the proportion of referred peers who initiated PrEP at three months, in Stata 16.1 using methods for cluster-randomized trials (cRCTs), where each cluster is a peer group of one index peer and three referred peers.

**Table 6** and **Figure 3** shows the power we attain to detect various increases in the proportion of referred peers who initiated PrEP in the enhanced group versus the standard. For our power calculations, we assumed 40 clusters (index peers) per group, 3 sampling units (referred peers) per cluster, and an intra-cluster correlation coefficient (ICC) of 0.05, which is standard for cRCTs, we might have 80% power to detect a difference of 17% PrEP initiators between the enhanced group (80%) and standard group (63%).

**Figure 3. Power calculation to detect increase in the percentage of referred peers initiating PrEP in the enhanced group compared to the standard.**

**Table 6. Increase in the % of referred peers initiating PrEP in the enhanced group compared to standard under different assumptions.**

Power	Standard: % PrEP initiation	Enhanced: % PrEP initiation	% increase
80%	57.1%	75.0%	17.7%
	63.0%	80.0%	17.0%
	69.1%	85.0%	15.7%
85%	55.8%	75.0%	19.2%
	61.7%	80.0%	18.3%
	67.9%	85.0%	17.10%
90%	54.2%	75.0%	20.8%
	60.1%	80.0%	19.9%
	66.4%	85.0%	18.7%

Assumptions: ICC: 0.05; clusters (providers) per arm: 40; units (clients) per cluster: 3 (75% of suggested clients referred)

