### ***10.2. Effect size estimation***

Our main analysis will evaluate the difference in proportion of PrEP initiation between referred peers in the enhanced and standard groups, as reported by index peers at Month 3. Secondarily, among referred peers at Month 3, we will evaluate the difference in proportions for recent HIV testing (since referral) and PrEP continuation (i.e., PrEP refilling) and median difference for self-reported PrEP adherence (using 100-point validated scale).

Our analysis is prespecified as intention to treat (ITT), using complete-case information and standard errors clustered at the level of the peer provider. We will estimate risk differences (RD) with 95% confidence intervals (CI) for binary outcomes using mixed-effect models with Gaussian distributions, identity links, study group fixed effects, and index peer random effects to adjust for clustering. For continuous outcomes, we will estimate median differences (MDs) using linear quantile mixed methods with the same specifications as those described above.

All the analyses will consider an alpha level of 0.05 as significant and will be run in R Studio (RStudio: Integrated Development Environment for R. Posit Software, MA 2025).

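### The SAP 10.4 arm effect on continuation among initiators is not a randomised comparison and does not test the robustness of the unconditional continuation result

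*SAP*

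**What the plan says.** SAP Table 3 defines continuation among referred peers as the share who returned for a refill out of all those referred. Its first footnote records that in v1.5 "this was conditional among clients who initiated PrEP, but we changed to make it unconditional". The change was made before unblinding, on the DSMB's recommendation, to agree with intention to treat and good trial practice. Protocol Table 8 also uses the number of referred clients as the denominator.

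SAP 10.4 then brings the conditional version back as a sensitivity analysis: "Measure effect estimates for peer client PrEP continuation as reported by index peers, among referred peers that initiated PrEP". Under SAP 10.2, binary outcomes receive a risk difference with a 95% CI, and "All the analyses will consider an alpha level of 0.05 as significant". The item carries no caveat, bounding method or descriptive-only label.

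The group it conditions on is formed by the primary outcome: "Our main analysis will evaluate the difference in proportion of PrEP initiation between referred peers in the enhanced and standard groups".

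**The concern.** Randomisation balances the arms before initiation, not after it. If the enhanced model works, its initiators include women who would not have started under standard referral, and the standard arm's initiators have no counterpart to them. A difference in refilling between the two groups then mixes any effect of the model on refilling with a difference in who was admitted to the denominator.

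The label adds to the problem. A sensitivity analysis should ask the same question under other assumptions. This one asks a different question, so agreement with the unconditional result would not support that result and disagreement would not undermine it. Protocol Table 8 sets a progression metric for client continuation (an increase of more than 20%). A sensitivity analysis pointing the other way could be misread as showing that the secondary result is fragile.

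**Working it through.** **Inputs from the documents.** SAP 5.1: "we assumed 40 clusters (index peers) per group, 3 sampling units (referred peers) per cluster, and an intra-cluster correlation coefficient (ICC) of 0.05", with 63% initiating in the standard group and 80% in the enhanced group at 80% power. Allocation is "1:1 enhanced group: standard group" (SAP Table 1). Tests are two-sided at 0.05 (Protocol, Statistical analysis; SAP 10.2).

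**The plan's own figure.** There are 40 × 3 = 120 referred peers per arm. The design effect is 1 + (3 - 1) × 0.05 = 1.10, so the effective number is 120 / 1.10 = 109.1 per arm. A two-proportion test of 63% vs 80% with pooled null variance gives power of 79.9%, which reproduces the stated 80%.

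**Who is compared.** Initiators number 120 × 0.63 = 75.6 in the standard arm and 120 × 0.80 = 96 in the enhanced arm. The added initiators are 120 × 0.17 = 20.4, which is 21% of the enhanced arm's initiators.

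**Assumptions, because the documents give no refill rates:**
- The same mix of women is referred in both arms.
- Every woman who would start under standard referral would also start under enhanced referral. These women refill at rate a in both arms.
- The added 17% refill at rate q.

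No woman then refills less because of the enhanced model.

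**Formulas.**
- Among initiators: standard = a; enhanced = (0.63a + 0.17q) / 0.80; RD = 0.17(q - a) / 0.80 = 0.2125(q - a).
- Among all referred: standard = 0.63a; enhanced = 0.63a + 0.17q; RD = 0.17q.

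**Worked case, a = 60%, q = 30%.**
- All referred: 0.63 × 0.60 = 37.8% vs 0.378 + 0.17 × 0.30 = 42.9%, RD +5.1 points.
- Initiators: 60.0% vs 0.429 / 0.80 = 53.6%, RD -6.4 points.
- Precision among initiators: effective numbers 75.6 / 1.10 = 68.7 and 96 / 1.10 = 87.3. SE = √(0.60 × 0.40 / 68.7 + 0.536 × 0.464 / 87.3) = 0.080. The expected 95% CI is about -22 to +9 points.
- Under a normal approximation the estimate is negative about 79% of the time and nominally significant for harm about 12% of the time, against 2.5% if the true difference were zero.

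Using 1.10 here assumes that the planning ICC and cluster size carry over to refills among initiators.

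**Range.**

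| a | q | RD among initiators | RD among all referred |
|---|---|---|---|
| 70% | 0% | -14.9 | 0 |
| 70% | 70% | 0 | +11.9 |
| 60% | 30% | -6.4 | +5.1 |
| 50% | 20% | -6.4 | +3.4 |
| 30% | 0% | -6.4 | 0 |
| 30% | 30% | 0 | +5.1 |
| 20% | 10% | -2.1 | +1.7 |

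For a from 30% to 70% and q from 0 to a, the conditional RD lies between 0 and -14.9 and the unconditional RD between 0 and +11.9. If q exceeds a, the conditional RD is positive although the model has changed nobody's refilling once started. For example, a = 50% and q = 70% gives 0.2125 × 0.20 = +4.3 points.

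**The case against.** The strongest reply is that the matter has largely been dealt with. The secondary outcome is unconditional in both documents. What remains is one of six sensitivity items, its denominator is stated, and keeping the superseded definition visible serves transparency. That stands, and it limits the severity.

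A reader might infer that this analysis is likely to contradict the main continuation result. The documents do not support that. In the worked case the expected intervals are about -22 to +9 among initiators and about -8 to +18 among all referred, so the usual outcome is two inconclusive, overlapping results. The only information on continuation is the remark in a SAP Table 3 footnote that it was low in data pooled across arms. This makes 60% look high; at 20% and 10% the conditional RD is only -2.1 points.

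A reader might also infer that the sign reverses by construction. It does not. Reversal needs added initiators to refill less and the model to have little effect on other women's refilling. Neither is documented, and the protocol's enhanced training includes reminders about consistent use. In the worked case, raising refilling among the 63% to (0.60 × 0.80 - 0.17 × 0.30) / 0.63 = 68.1% in the enhanced arm cancels the negative result.

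Finally, referred peers are themselves chosen after randomisation (SAP 6.1), so a table over all referred peers is not fully protected either. That also stands, and the fix allows for it.

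**Conclusion.** The concern holds as a minor point of estimand and labelling. The comparison among initiators conditions on a post-randomisation outcome that the trial is designed to change. It has no randomised interpretation and cannot serve as a robustness check on the unconditional result. Under the stated assumptions the distortion runs from 0 to -14.9 points, is about -6 points at 60% and 30%, and is about -2 points at the lower rates of 20% and 10%. It disappears if added initiators refill at the same rate as the others and favours the enhanced arm if they refill more. All of these sizes rest on assumed refill rates and on planning initiation of 63% vs 80%.

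A reader might go further and conclude that the trial's continuation finding is compromised, or that the enhanced model harms women who start PrEP. Neither follows: the secondary outcome already avoids this conditioning, and the documents contain no refill data by arm.

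**What to change.** In SAP 10.4, move this item out of the sensitivity analyses and label it a supplementary, descriptive, non-randomised summary. Report the number and proportion refilling among initiators in each arm, without an arm effect estimate, CI or p-value.

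Beside it, tabulate by arm: not initiated, initiated without refill, refilled. Show this over all referred peers and also over the fixed base of four per index peer (n=320) that 10.4 already plans, counting unfilled places as not initiated. The fixed base does not depend on how many peers each arm refers. Apply the 10.3 rule for don't-know answers and state how many were reclassified.

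The cost is a change of SAP wording and one table from data already collected. The sponsor gives up one between-arm estimate; the unconditional secondary analysis is unchanged.

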## **10.5 Adverse events**

The total number of adverse events will be reported by randomization group and severity. The proportion of participants with the following events will be compared using chi-square or Fisher’s exact test:

- Physical violence, assault, or abuse
- Non-physical harassment or assault
- Unintentional or unauthorized disclosure of HIV status
- Suicidal thoughts or ideation
- Death

Serious adverse events (including any instance of violence, suicidality, or death) will be reported to the DSMB within 24 hours, including a report of the circumstances surrounding the adverse event. The randomization group of the participant will be communicated by the study statistician (CC) to the DSMB.

All serious and non-serious adverse events will be included in interim and final monitoring reports.

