Implementation outcomes. Additionally, in all follow-up surveys among peer providers and clients we will measure a number of implementation outcomes including participants' perceptions of the intervention's

882 acceptability, feasibility, and appropriateness. To measure these outcomes, we will use validated scales
 883 and established theories/frameworks adapted to the Kenyan setting and to young women (e.g., the
 884 Theoretical Framework of Acceptability). Additionally, at follow-up, we will have peer clients complete a
 885 checklist of materials received from peer providers to measure “fidelity” of the intervention in both
 886 intervention arms.

887 Costs are another important implementation outcome we plan on measuring during this trial. To measure
 888 costs, we will micro-cost the formal delivery model and compare the incremental cost of this model with
 889 the existing informal referral strategy (Objective 4). Activity-based micro-costing will be conducted for
 890 costs incurred (e.g., HIVST kits) and costs averted (e.g., personnel). We will use time and motion studies
 891 to measure staff time spent training peer providers. Estimates of cost using the activity-based approach
 892 will be compared with the top-down approach (i.e., the budget divided by the number of peer providers
 893 and peer clients)^{74 75 76 77} (**Table 9**).

894 **Safety.** We will measure “safety” of the intervention by
 895 screening for PrEP side effects (i.e., nausea, vomiting,
 896 headache) among peer clients (and as reported by both peer
 897 provider and clients) and any reports of social harm (e.g.,
 898 physical, verbal, emotional violence) related to our delivery
 899 model (Objective 4).

Table 9. Description of costing inputs

Costs: Start-up: microplanning, training, mobilization;

Recurrent: personnel, capital, supplies, overhead

Data: Project budget; time & motion; staff interviews;
published literature; central price list & salaries

Unit cost: Cost/PrEP users trained, peer referred, peer
initiated on PrEP, peer retained on PrEP.

900 The findings from this trial (described above) will be used to inform a NIH R01 proposal for a peer PrEP
 901 referral + HIVST community-randomized trial and budget impact analysis.

902 *Statistical analysis*

[figure not shown]
903 We will measure effect size estimates using mixed effects multilevel regression models (primary

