## 6. Randomization and masking

## **6.1. Randomization**

Randomization list. A Fred Hutch statistician will prepare a list of randomization assignments for index peers with block sizes of 4. This list will be stored in a password-protected electronic file on a Fred Hutch server.

Randomization implementation. Index peers will be randomized at enrollment, which will occur at Month 0. Then, referred peers will be chosen by index peers. At the time of randomization, index peers will open an opaque randomization envelope, given to them by a study research assistant, that has their study arm assignment inside.

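### The adverse-event tests in SAP 10.5 ignore the index-peer cluster, so p-values can be too small when events are not rare, and PrEP side effects have no defined place in the safety analysis.

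*SAP*

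**What the plan says.** **Safety test.** SAP 10.5 reports the total number of adverse events by group and severity. It then lists physical violence, non-physical harassment, disclosure of HIV status, suicidal thoughts and death: "The proportion of participants with the following events will be compared using chi-square or" Fisher's exact test. The unit is the participant. The comparison is not limited to index peers.

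**Design.** SAP 3.2 describes a two-arm cluster-randomised trial. SAP 6.1 states: "Index peers will be randomized at enrollment, which will occur at Month 0". Index peers then choose whom to refer. SAP 5.1 bases power on a design "where each cluster is a peer group of one index peer and three referred peers".

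**Clustering elsewhere.** SAP 10.2 uses clustered standard errors and "index peer random effects to adjust for clustering". The Protocol's Statistical analysis section sets a general rule that peer-client analyses adjust standard errors for clustering by peer provider.

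**Side effects.** The Safety paragraph of the Protocol's Aim 2 Data Analysis section measures safety in two ways. One is "screening for PrEP side effects (i.e., nausea, vomiting" and headache) among peer clients, reported by providers and clients. The other is social harm. Study oversight in the Protocol has the monitoring committee review side effects, SAEs and social harms by arm.

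**The concern.** Women referred by the same index peer share her arm, her conduct and often a social circle. Harassment, violence or unwanted disclosure can reach several of them at once, and the Protocol's Risks section itself notes that a peer-delivered model makes involvement more likely to become known. A test that counts these women as independent overstates the information in the data. At stake is the stated significance of any difference in harms between arms.

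The second issue is completeness. Social harm, one half of the Protocol's safety measure, is covered by the SAP list. PrEP side effects, the other half, are not named there. The SAP's overall adverse-event total does not clearly include them, because Study oversight in the Protocol describes adverse events as forms of abuse.

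**Working it through.** **Inputs.** SAP 5.1 states: "we assumed 40 clusters (index peers) per group, 3 sampling units (referred peers) per cluster". It also gives an "intra-cluster correlation coefficient (ICC) of 0.05, which is standard for cRCTs". That ICC is for PrEP initiation; neither document gives one for harms. Alpha is 0.05 (SAP 10.2), two-sided (Protocol, Statistical analysis).

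**Step 1: reproduce the plan's own clustering calculation.** The SAP claims 80% power for 63% against 80%.
- Design effect DE = 1 + (3 − 1) × 0.05 = 1.10.
- Effective n per arm = 40 × 3 / 1.10 = 109.1.
- Two-proportion power with pooled variance = 79.85%. The claim reproduces. Without the design effect, power would be 83.5%, so the plan did allow for clustering here.

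**Step 2: large-sample size of an unadjusted chi-square test.** True size = 2 × [1 − Φ(1.96/√DE)], with DE = 1 + (m − 1) × ICC and m the number of women per cluster. For m = 4 (one index peer and three referred peers):

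| ICC | DE | 1.96/√DE | True size |
|---|---|---|---|
| 0.05 (plan) | 1.15 | 1.828 | 6.8% |
| 0.10 (assumed) | 1.30 | 1.719 | 8.6% |
| 0.20 (assumed) | 1.60 | 1.549 | 12.1% |

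At ICC 0.05 the size is 5.6% for m = 2, 6.2% for m = 3 and 7.4% for m = 5.

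**Step 3: does this hold for sparse events and for Fisher's test?** Beta-binomial simulation, 40 clusters per arm, four women per cluster, no true difference, 40,000 runs per row. Event rates are assumptions, since the documents give none. The last column is a t-test on cluster totals.

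| ICC | Event rate | Chi-square | Fisher | Cluster-level test |
|---|---|---|---|---|
| 0.05 | 2% | 5.9% | 1.9% | 4.7% |
| 0.05 | 5% | 6.5% | 3.6% | 4.7% |
| 0.05 | 10% | 6.9% | 4.7% | 4.9% |
| 0.05 | 20% | 7.0% | 5.2% | 5.1% |
| 0.20 | 2% | 11.1% | 4.7% | 3.1% |
| 0.20 | 5% | 11.5% | 7.4% | 4.5% |
| 0.20 | 10% | 12.3% | 9.2% | 4.9% |
| 0.20 | 20% | 12.5% | 9.9% | 5.2% |

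The SAP does not say when each test applies. A common rule is Fisher when the expected count per arm is below 5, otherwise chi-square. At ICC 0.05 this gives sizes of about 0.6%, 2.4% and 4.4% at event rates of 1%, 2% and 3%, and 6.3% to 7.0% at rates of 5% and 10%.

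**Step 4: side effects, texts set side by side.**
- Protocol, Safety paragraph (Aim 2): side effects are measured among peer clients.
- Protocol, Study oversight: side effects are reviewed by arm, but adverse events are described as forms of abuse.
- Protocol, SAFETY section under PrEP: only SAEs are documented.
- SAP 10.5: side effects are not named; all serious and non-serious events go into monitoring reports.

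These cannot all be followed as written. The SAE definitions also differ: hospitalisation or death in the Protocol; violence, suicidality or death in the SAP.

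**The case against.** The listed harms are likely to be rare, so Fisher's test would often be used, and it is conservative there. At ICC 0.05 with four women per cluster its simulated size is below 5% for event rates up to 10%. This stands. A reader might infer that the safety p-values are too small across the board, and the documents do not support that. They allow Fisher as well as chi-square, and they state no event rate and no ICC for harms. What remains is that the two errors offset only by accident, and inflation returns with commoner events or stronger clustering.

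Four women per cluster is a planning value. SAP Table 1 warns that referred-peer enrolment may be lower, and smaller clusters reduce the inflation. Index peers analysed alone, one per cluster, are unaffected. Both points stand.

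An unadjusted harms test errs, if at all, toward flagging harm, and no success claim or stated decision rule rests on it. That limits the consequence but does not make the method fit the design.

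A reader might also infer that side effects would go unreported by arm. That goes too far: Study oversight in the Protocol has the monitoring committee review them by arm. What is missing is a defined place in the final analysis. Nor is another significance test needed. Side effects arise only in women who take PrEP, so comparing them across all referred peers would partly repeat the primary outcome.

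**Conclusion.** The point holds as a minor one. The tests in SAP 10.5 ignore the randomised cluster, against the SAP's own design and the Protocol's rule for peer-client analyses. A nominal 5% chi-square test has a true size of about 6.8% when events are not rare. This assumes four women per cluster and that the ICC of 0.05 for PrEP initiation carries over to harms. The 8.6% and 12.1% figures rest on ICCs that the documents do not give. With Fisher's test on rare events there is no inflation at ICC 0.05.

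Separately, PrEP side effects are a declared safety measure that SAP 10.5 does not place, and the Protocol's statements on which events are documented conflict. Neither issue touches the primary result.

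**What to change.** 1. In SAP 10.5, replace the chi-square and Fisher tests with a permutation test that re-randomises whole index-peer clusters within the randomisation blocks of 4 (SAP 6.1). It remains usable with few events. Where events suffice, the cluster-adjusted risk-difference model of SAP 10.2 is an alternative.
2. Tabulate index peers and referred peers separately.
3. Add a descriptive table of PrEP side effects by arm and by reporter (provider or client), without a test.
4. Reconcile the Protocol's Safety paragraph, its SAFETY section (only SAEs documented) and Study oversight (adverse events as abuse, side effects reviewed by arm) with SAP 10.5, including the two SAE definitions.

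The cost is a few lines of code, slightly wider intervals and a short text amendment. No new data are needed if side-effect screening goes ahead as the Safety paragraph plans.
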